5.8 Treatment compliance - amended

5.8.1 Rivaroxaban

Instruction will be given to return all unused study drug including packaging, if applicable, at Visit 3, Visit 4, and, if applicable, at the premature discontinuation visit. Compliance will be evaluated by measuring remaining suspension. All non-used study medication should be kept securely in the original containers in a designated locked container until retrieved or dispensed.³³

³³ Comparator arm was removed via Amendment 4 (see Section [16.2.2.20](#), [16.2.2.21](#), [16.2.2.22](#), [16.2.2.23](#) and [16.2.2.24](#))

6. Study Procedures

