4.5.2 Compliance

4.5.2.1 Rivaroxaban

Overall compliance will be calculated for the actual treatment period (final stop date minus start date + 1 day) as total volume of suspension taken divided by the total volume of suspension to be taken considering required dose (volume) given the weight of the child and b.i.d. regimen between the first intake and last intake dates in the main treatment period. The total volume of suspension taken will be derived as the sum of amount taken for each bottle dispensed. The amount administered from a bottle will be calculated as the difference between the dispensed and returned amount. If the difference would be negative then the amount administered will be 0 (the volume dispensed could be larger as nominal 45 mL). If the volume returned is missing, but the investigator stated in the CRF that the patient took all medications not returned then the amount of taken will be the amount of dispensed. If the amount administered is also given then this will be considered. If the volume of dispensation taken by the patient cannot be determined for a bottle, because no bottle is returned and the amount administered is not stated, it will be assumed that the prescribed amount of study medication has been taken from the bottle unless the investigator commented it explicitly as non-compliance.

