5.1 Assignment of analysis sets

Final decisions regarding the assignment of subjects to analysis sets will be made during the review of study data and documented in the final list of important deviations, validity findings and assignment to analysis set(s) (see Section 4.6).

Full analysis set: This analysis set will include all enrolled children (except screening failures).

Safety analysis set: This analysis set will include all enrolled children who received at least one dose of study medication.

Per protocol set: This population includes all enrolled children who had at least 25 days study treatment. Children who discontinued study treatment earlier than 25 days due to an efficacy or bleeding outcome or due to death or due to a procedure defined in the study protocol or withdrew consent will not be excluded from the per protocol set. Children with a calculated compliance less than 50% will be excluded from the per protocol set, calculated

compliance between 50% and less than 80% and greater than 120% is considered as minor protocol deviation. These definitions are considered as clarifications to the definitions in the study protocol. The per protocol set may also exclude other major protocol deviations. Further details will be specified in the in the Protocol Deviation Document and in the Validity Review Report.

In addition to the analysis population defined in the study protocol, the following population will be used as well.

All subjects with at least 1 PK sample in accordance with the PK sampling strategy will be included in the PK analysis (PK analysis set).

All subjects with at least 1 blood sample for clotting parameters in accordance with the PD sampling strategy will be included in the PD analysis (PD analysis set).

Listing only set: This population includes all screening failures.

6. Statistical Methodology

Treatment groups will be displayed as study medication administered.

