6.7 Taste and texture questionnaire

Results for the taste-and-texture questionnaire in children older than 4 years who receive the oral suspension will be presented descriptively as counts and proportions of responses by questions.

7. Document history and changes in the planned statistical analysis

First draft of SAP was circulated with the Bayer team on 10 Dec 2014.

Version 1.0: 26 Jun 2015.

SAP Version 2.0 dated 28 Apr 2017 was prepared to provide the following edits. None of them are considered to change the primary efficacy analysis and other analyses as described, but includes additional analyses and further clarifications:

- There is a typo in the date of Version 1.0: it was finalized on 26 Jun 2015 and not in 2014.
- No by visit compliance will be calculated, because drug accountability data were not to be recorded at visit 3. The calculations of compliance were further specified.
- The definition of the per protocol set was updated based on the decisions of the blind review meetings: This population includes all enrolled children who had at least 25 days study treatment. Children who discontinued study treatment earlier than 25 days due to an efficacy or bleeding outcome or due to a procedure defined in the study protocol or withdrew consent will not be excluded from the per protocol set. If a child died having less than 25 days study treatment, they will not be excluded from the per protocol set. Children with a calculated compliance less than 50% will be excluded from the per protocol set, calculated compliance between 50% and less than 80% and greater than 120% is considered as minor protocol deviation.
- Added PK analysis set and PD analysis set based on the decisions of the blind review meetings.
- Treatment groups will be displayed as study medication administered.
- Antithrombotics started after stop of study medication will be displayed only.
- Analysis of demographic, medical history and efficacy was further clarified, analysis of and PK/PD data by weight was included.
- Sensitivity analysis as described in Section 6.3.1 will be done only if at least one confirmed recurrent event occurred within the 30 days intended treatment period.

8. References

1. The EINSTEIN investigators. Oral Rivaroxaban for Symptomatic Venous Thromboembolism. *N Engl J Med* 2010; 363: 2499-2510.

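### Unreturned bottles with no stated intake are scored as the full prescribed amount, which can keep a child with low measured compliance in the per protocol set

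*SAP*

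**What the plan says.** - **Basic calculation.** SAP 4.5.2.1 divides the volume taken by the volume that should have been taken over the actual treatment period. Intake per bottle is the dispensed amount less the returned amount.
- **Returned volume missing, investigator states that everything not returned was taken.** In that case "then the amount of taken will be the amount of dispensed".
- **Intake undeterminable** "because no bottle is returned and the amount administered is not stated". Here "it will be assumed that the prescribed amount of study medication has been taken from the bottle", "unless the investigator commented it explicitly as non-compliance".
- **Use of the result.** SAP 5.1: "Children with a calculated compliance less than 50% will be excluded from the per protocol set". Values from 50% to below 80% are a minor deviation. SAP 6.5.1.2 tabulates compliance in categories, one of which is Missing.
- **Visit 3.** SAP section 7 drops by-visit compliance "because drug accountability data were not to be recorded at visit 3". Protocol 5.8.1 reads: "Instruction will be given to return all unused study drug including packaging, if applicable, at Visit 3, Visit 4". Protocol 6.4 and the flow chart (Figure 1-1) both list drug accountability and a compliance check at Visit 3.

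**The concern.** Protocol 5.8.1 bases compliance on the measured remaining suspension. A bottle that never comes back has no measurement, and the SAP fills the gap with the most favourable plausible value. A site that says nothing about the bottle is treated as reporting full intake. Failure to return a bottle may itself go with poor adherence, so the rule is most generous where the data are weakest.

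Nor is the imputation visible in the planned tables. SAP 4.3 commits to counting missing repeat imaging, laboratory and weight values, but not undetermined bottles. A reader of the compliance table could not tell measured from assumed compliance. With 20 planned children, 10 per age group, one child who changes status is 5% of the total or 10% of an age group.

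**Working it through.** The plan states no figure to reproduce, so the check works through the rule itself.

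**Inputs from the documents**
- Dose at 12 to <20 kg: 4.0 mg twice daily (Protocol Table 5-1)
- Concentration: 1 mg/mL (Protocol 5.4.1)
- Duration: 30 days (Protocol 5.3)
- Nominal bottle: 45 mL (SAP 4.5.2.1)
- Exclusion limit: 50% (SAP 5.1)

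**Assumptions, because the documents give no values**
- c = compliance on the accounted bottles
- u = share of the prescribed volume that falls in unreturned, undocumented bottles
- The child meets the other per protocol conditions.

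**Formulas**
- SAP compliance = c(1 − u) + u
- Lower bound, nothing taken from those bottles = c(1 − u)
- The SAP value reaches 50% once u ≥ (0.5 − c)/(1 − c)

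**Worked example**
1. Course volume: 2 × 4.0 mg ÷ 1 mg/mL × 30 = 240 mL.
2. One bottle prescribed in full: u = 45/240 = 18.75%.
3. With c = 40%, the limit is crossed at u = 0.10/0.60 = 16.7%, so this one bottle is enough.
4. SAP value: 0.40 × 0.8125 + 0.1875 = 0.5125, or 51.25% (kept, minor deviation).
5. Accounted bottles only: 40% (excluded). Lower bound: 0.40 × 0.8125 = 32.5% (excluded).

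The result depends on which bottle is missing. If bottles are used up in turn, five cover 225 mL and a sixth covers 15 mL. If only the sixth is missing, u = 15/240 = 6.25% and the SAP value is 0.375 + 0.0625 = 43.75%, still excluded.

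**Range at c = 40%**

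| u | SAP value | Lower bound |
|---|---|---|
| 10% | 46% | 36% |
| 25% | 55% | 30% |
| 50% | 70% | 20% |
| 75% | 85% | 10% |

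At u = 100% the SAP value is 100% with nothing measured. For other values of c, the 50% limit is crossed at u = 28.6% (c = 30%) and u = 50% (c = 0).

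**Weight of one full bottle**

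| Body weight | 30-day volume | One 45 mL bottle as a share |
|---|---|---|
| 3 to <4 kg | 42 mL | 100% (one bottle covers the course) |
| 6 to <7 kg | 108 mL | 42% |
| 8 to <10 kg | 192 mL | 23% |
| 12 to <20 kg | 240 mL | 19% |
| 20 to <30 kg | 300 mL | 15% |
| 30 to <50 kg | 450 mL | 10% |

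**Direction.** SAP value minus c equals u(1 − c), which is zero or positive when c ≤ 100%. Only if the other bottles exceed 100% would the rule pull the figure down towards 100%.

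**The case against.** The rule is narrower than a quick reading suggests. It needs a bottle that was not returned, no stated amount and no investigator comment of non-compliance, and it imputes the prescribed amount, not the bottle's contents. The investigator comment is a real safeguard, and the study booklet (Protocol 6.13) tracks drug intake, so a long gap might well be noticed. SAP 4.3 also sets out a general preference for rules that avoid losing subjects to incomplete data. The number of such bottles may be zero. All of this stands and limits the size of the point. It does not change the direction of the rule or make the imputation visible.

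Three stronger readings are tempting, and the documents do not support them.

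- **That the Visit 3 gap turns first-half bottles into full compliance.** A bottle handed back at Visit 3 has been returned, so it does not meet the condition "because no bottle is returned and the amount administered is not stated". SAP section 7 links the gap only to by-visit compliance, and nothing says that those volumes were never measured or never entered later. A child with no intake at all before Visit 3 would also conflict with Protocol 6.3, under which the first dose is given at Visit 2. What does stand is a gap: no rule covers a bottle returned without a recorded volume when the investigator has not stated intake.
- **That the Missing category can no longer occur.** That uncovered case could still produce a missing value. So could an unreturned bottle with a non-compliance comment but no amount.
- **That the bleeding result is affected.** SAP 6.2 uses the safety analysis set and a window ending 2 days after the stop of study medication, with no compliance filter.

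**Conclusion.** The point holds as a minor one. SAP 4.5.2.1 uses a one-directional, best-case imputation that can move a child across the 50% limit. In the example the same child has 51.25% under the SAP rule and 32.5% at the lower bound. This rests on an assumed 40% compliance on accounted bottles, one missing bottle whose full 45 mL was prescribed, and a 30-day course. How often this occurs cannot be derived from the documents.

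The reach is limited to the compliance table (SAP 6.5.1.2), the per protocol summary of treatment duration (SAP 6.5.1.1) and the supportive per protocol efficacy analysis (SAP 6.3). The primary outcome is unaffected. Independently of the imputation, the SAP's statement that "drug accountability data were not to be recorded at visit 3" contradicts Protocol 5.8.1, 6.4 and the flow chart.

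**What to change.** 1. Keep the rule in SAP 4.5.2.1 if it is wanted, but report the number of children and of bottles to which it was applied.
2. Show the compliance categories and per protocol membership twice, with undetermined bottles counted as taken and as not taken. If membership differs, repeat the supportive efficacy summary for the second set. This is preferable to setting a child to Missing because of a single bottle, which would discard the measured bottles.
3. State how a bottle returned without a recorded volume enters the calculation, and when the Missing category applies.
4. Reconcile SAP section 7 with Protocol 5.8.1, 6.4 and the flow chart, and state how drug returned at Visit 3 is used.

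The cost is SAP wording, one or two extra table rows and a less favourable lower bound for compliance; if membership changes, the supportive efficacy summary is run a second time. No new data collection is needed.

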4.5.2.2 LMWH or Fondaparinux

This section is applicable only if a patient received LMWH or Fondaparinux as study medication before Protocol Amendment 4.

The visit compliance will be calculated as number of syringes administered divided by number of syringes to be administered between the two visits considering b.i.d. or o.d. regimen given the medication. In addition, Overall compliance will be calculated for the 30

days treatment period as total number of syringes administered divided by the total number of syringes to be administered considering b.i.d. or o.d. regimen between the first intake and last intake dates in the main treatment period.

4.5.2.3 Vitamin K antagonists

This section is applicable only if a patient received VKA as study medication before Protocol Amendment 4.

The Integrated Protocol states that at least one international normalized ratio (INR) measurement is required per two weeks. For calculation of compliance, the following rules will be applied:

The treatment period will be split up in periods of 14+5=19 days. If the last period is shorter than 15 days, the actual length relative to 19 days will be calculated, i.e. less than one (for example, if the subject stopped study medication on day 22, his 2nd period had a relative length of $(22-19)/19=0.16$). The number of these periods will be the denominator for the calculation of compliance including the last period which can be numerically less than one. Using the example above, the subject's denominator would be 1.16 (i.e. less than 2 full periods). If a subject received study medication for less than 19 days, the denominator will be one.

For the numerator it will be counted in how many periods INR measurements were done.

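### The VKA compliance formula in SAP 4.5.2.3 can exceed 100%, so a fully monitored 30-day child scores 127% and is labelled a minor protocol deviation

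*SAP*

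**What the plan says.** SAP 4.5.2.3 starts from the requirement that "at least one international normalized ratio (INR) measurement is required per two weeks". It then builds the denominator: "The treatment period will be split up in periods of 14+5=19 days". A short final period is scaled: "If the last period is shorter than 15 days, the actual length relative to 19 days will be calculated, i.e. less than one". The SAP illustrates this with a child who stops on Day 22, whose second period has relative length 0.16, and concludes that "the subject's denominator would be 1.16". A child treated for less than 19 days has a denominator of one. The numerator rule is a single sentence: "For the numerator it will be counted in how many periods INR measurements were done".

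SAP 5.1 applies thresholds to calculated compliance. Below 50%, the child leaves the per protocol set. Otherwise, "compliance between 50% and less than 80% and greater than 120% is considered as minor protocol deviation". The rule does not separate VKA from rivaroxaban. SAP 6.5.1.2 tabulates compliance as missing, below 50%, 50% to below 80%, and 80% or more, with no upper limit on the last row.

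SAP 4.5.2.3 covers only children given VKA as their study drug before Amendment 4. The amendment overview in Protocol 16.2.1.2 says that data from comparator children treated before the amendment will still be analysed and reported.

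**The concern.** The same short last period is counted in two ways. With an INR in it, it adds 1 to the numerator and less than 1 to the denominator, so perfect monitoring does not come out at 100%. A ratio above 100% can mean something for suspension volume, where a child may take too much. For the share of periods with an INR it means nothing.

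At stake is how a deviation is classified. The 120% limit in SAP 5.1 would catch VKA children because of the formula and not because of anything that happened to them. This is not confined to early stoppers: it occurs at the planned duration of 30 days.

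**Working it through.** **Inputs.** Period length 19 days; a last period under 15 days counts as its days divided by 19; the numerator is a whole-number count of periods with an INR (all SAP 4.5.2.3). Thresholds are 50%, 80% and 120% (SAP 5.1). Planned treatment is 30 days (Protocol 5.3), and Visit 4 is at Day 30 ± 3 (Protocol 6.1). A last period of 15 days or more is taken as one full period, which the SAP implies.

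**Reproducing the SAP's example (stop on Day 22).** (22 − 19)/19 = 0.158, which rounds to 0.16. The denominator is 1 + 0.158 = 1.158, which rounds to 1.16. Both match the SAP. The SAP does not go on to the score: with an INR in both periods it is 2/1.158 = 172.7%.

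**General form.** For a stop day D from 20 to 33, the denominator is 1 + (D − 19)/19 = D/19. With an INR in both periods the score is 2/(D/19) = 38/D. With an INR in only one period it is 19/D.

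| Stop day | Denominator | INR in both periods | INR in one period |
|---|---|---|---|
| 20 | 1.053 | 190.0% | 95.0% |
| 22 | 1.158 | 172.7% | 86.4% |
| 27 | 1.421 | 140.7% | 70.4% |
| 28 | 1.474 | 135.7% | 67.9% |
| 29 | 1.526 | 131.0% | 65.5% |
| 30 | 1.579 | 126.7% | 63.3% |
| 31 | 1.632 | 122.6% | 61.3% |
| 32 | 1.684 | 118.8% | 59.4% |
| 33 | 1.737 | 115.2% | 57.6% |
| 34 to 38 | 2 | 100.0% | 50.0% |

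**Where the 120% limit is crossed.** 38/D > 1.20 requires D < 31.67, so the flag applies to stop days 20 to 31. Within the Visit 4 window (Days 27 to 33), five of the seven stop days are flagged.

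**Possible corrections, tested at Day 30.**
- Cap at 100%: an INR in both periods gives min(126.7%, 100%) = 100%. An INR in one period stays at 63.3%.
- Weight each covered period by its length: both periods give (1 + 0.579)/1.579 = 100%. An INR in the first period only gives 1/1.579 = 63.3%. An INR in the last 11 days only gives 0.579/1.579 = 36.7%, which is below 50% and so a per protocol exclusion.

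**The case against.** The strongest reply is that the consequence is one label. A score above 120% is a minor deviation and does not remove the child from the per protocol set. Bleeding is analysed on the safety set (SAP 6.2) and efficacy on the full analysis set, with the per protocol analysis only supportive (SAP 6.3). Standard-of-care children are shown separately, and final set assignment is left to data review (SAP 4.6 and 5.1). All of this stands, and it limits the weight of the point.

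It can also be argued that the numerator was meant to be fractional, since the SAP calls the fractional total a number of periods: "The number of these periods will be the denominator for the calculation of compliance including the last period which can be numerically less than one". On that reading full monitoring gives 100%. But the wording about less than one is attached to the denominator only, so the reading cannot be relied on.

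A reader might infer that no 30-day VKA child can ever be counted as compliant, because the only possible scores are 126.7%, 63.3% and 0%. The documents do not support that. The 126.7% child is tabulated with all others at 80% or more. A score of 0% means no INR in 30 days, which is a real monitoring failure and not an artefact. Small changes in duration also matter: fully monitored children who stop on Day 32 or 33 are not flagged.

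**Conclusion.** The formula is wrong as written, and the error is minor. A VKA child with an INR in every period scores above 100% for stop days 20 to 33, and above 120% for stop days 20 to 31. In that second range SAP 5.1 calls a fully monitored child a minor protocol deviation while SAP 6.5.1.2 places the same child in the best compliance row.

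This rests on the literal numerator sentence and on SAP 5.1 applying to INR-based compliance, from which nothing in the SAP exempts it. Fully monitored here means an INR in each 19-day period, which is not identical to one INR per two weeks: INRs on Days 10 and 19 leave Days 20 to 30 empty and score 63.3% at Day 30. The Protocol Deviation Document and Validity Review Report, to which SAP 5.1 refers for details, are not available and might treat the matter differently.

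The documents do not say how many children received VKA as study drug; there may be none. It would be wrong to infer any effect on the rivaroxaban results, or on any safety or efficacy estimate.

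**What to change.** Add one sentence to SAP 4.5.2.3 stating that INR-based compliance is capped at 100%. The cap changes only scores above 100%, so every classification at the 50% and 80% limits stays as it is. Alternatively, state in SAP 5.1 that the criterion of more than 120% does not apply to INR-based compliance; this removes the false flag but leaves figures above 100% in the output.

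Do not weight the numerator by period length. That also gives 100% for full monitoring, but it would move a 30-day child with an INR only in the last 11 days from 63.3% to 36.7% and so out of the per protocol set.

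The cost is one sentence and, for the cap, one line of code. No new data are needed.

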4.6 Blind Review

The results of the final data assessment will be documented in the final list of important deviations, validity findings and assignment to analysis set(s). Any changes to the statistical analysis prompted by the results of the review of study data will be documented in an amendment and, if applicable, in a supplement to this SAP.

5. Analysis Sets

5.1 Assignment of analysis sets

Final decisions regarding the assignment of subjects to analysis sets will be made during the review of study data and documented in the final list of important deviations, validity findings and assignment to analysis set(s) (see Section 4.6).

Full analysis set: This analysis set will include all enrolled children (except screening failures).

Safety analysis set: This analysis set will include all enrolled children who received at least one dose of study medication.

Per protocol set: This population includes all enrolled children who had at least 25 days study treatment. Children who discontinued study treatment earlier than 25 days due to an efficacy or bleeding outcome or due to death or due to a procedure defined in the study protocol or withdrew consent will not be excluded from the per protocol set. Children with a calculated compliance less than 50% will be excluded from the per protocol set, calculated

compliance between 50% and less than 80% and greater than 120% is considered as minor protocol deviation. These definitions are considered as clarifications to the definitions in the study protocol. The per protocol set may also exclude other major protocol deviations. Further details will be specified in the in the Protocol Deviation Document and in the Validity Review Report.

In addition to the analysis population defined in the study protocol, the following population will be used as well.

All subjects with at least 1 PK sample in accordance with the PK sampling strategy will be included in the PK analysis (PK analysis set).

All subjects with at least 1 blood sample for clotting parameters in accordance with the PD sampling strategy will be included in the PD analysis (PD analysis set).

Listing only set: This population includes all screening failures.

6. Statistical Methodology

Treatment groups will be displayed as study medication administered.

